## 6.8. Safety Analyses

Safety analyses will be descriptive in nature. Summary statistics for each parameter at a specific visit, as well as the change from Baseline to that visit, will also be displayed. All safety data will be presented in the data listings.

#### 6.8.1 Adverse Events

The final analysis of 4658-102 AE will include all data collected in 4658-102.

In general, only TEAEs will be summarized. Nontreatment-emergent events will be recorded in the data listings. Unless noted otherwise, for all AE tables, the number and

percentage of patients reporting AEs will be grouped using the MedDRA System Organ Class (SOC) and Preferred Term (PT) and summarized overall and by age cohort.

An overall summary table of adverse events will be produced and will include:

- The frequency count and percentage of patients with:
  - o A TEAE
  - A Treatment-related TEAE
  - A Severe TEAE
  - A Treatment-Emergent SAE
  - A Treatment-Emergent Related SAE
  - A TEAE leading to discontinuation of study drug
  - A TEAE leading to death
  - A Non-Serious TEAE
- The number of events
  - at each severity level (mild, moderate, severe)
  - that are non-serious
  - $\circ$  that are serious

Multiple occurrences of the same AE (at the preferred term level) in the same patient will be counted only once in frequency tables. If a patient experiences multiple episodes of the same event with different relationship/severity, the event with the strongest relationship or maximum severity to investigational drug product will be used to summarize AEs by relationship and severity.

The following summary tables will be produced:

- TEAEs by SOC and PT
- TEAEs by SOC, PT and severity
- TEAEs by descending frequency of PT
- Treatment-related TEAEs by SOC and PT
- Treatment-related TEAEs by SOC, PT, and severity
- Treatment-related TEAEs by descending frequency of PT
- TEAEs related to study procedures by SOC and PT
- TEAEs related to underlying disease by SOC and PT
- Treatment-Emergent SAEs by SOC and PT
- Treatment-related Treatment-Emergent SAEs by SOC and PT
- Non-Serious TEAEs by SOC and PT

In addition, all SAEs, regardless of their treatment-emergent status will be summarized.

The following listings will be produced:

- Non-treatment-emergent AEs
- All TEAEs
- AEs leading to discontinuation
- SAEs

Additionally, summary tables of AEs by each one-year duration of eteplirsen (i.e., AEs at the  $1^{st}$  year of eterplirsen treatment,  $2^{nd}$  year,  $3^{rd}$  year, ...,  $6^{th}$  year) will be provided.

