The dose-titration period will last 10 weeks overall (1 infusion/week) to slowly achieve the target dose of 30 mg/kg. Eteplirsen dosing will begin at 2 mg/kg for 2 weeks (Weeks 1 and 2) and will escalate to 4 mg/kg (Weeks 3 and 4), 10 mg/kg (Weeks 5 and 6), 20 mg/kg (Weeks 7 and 8), and 30 mg/kg (Weeks 9 and 10). Patients will continue to receive 30 mg/kg eteplirsen for the duration of the study. The duration of each patient's treatment in the study is expected to be at least 48 weeks (including the 10-week titration period), and patients may continue to receive treatment in the study for up to 96 weeks determined by the Investigator based on the absence of any safety signal and an indication of clinical benefit.

In addition, study drug may be interrupted or discontinued for specific safety reasons.

Safety will be regularly assessed throughout the study via the collection of AEs, clinical safety laboratory tests (blood chemistry, hematology, renal function, coagulation, and urinalysis), electrocardiograms (ECGs), echocardiograms (ECHOs), vital signs, and physical examinations.

Plasma and urine samples for PK assessments will be collected at Week 2 (2-mg/kg dose level), Week 6 (10-mg/kg dose level), Week 8 (20-mg/kg dose level), and at Weeks 10 and 24 (30-mg/kg dose level). Serial PK samples will be collected pre-dose, immediately prior to the end of infusion (prior to flush), and approximately 1-3 hours and 6-8 hours after completion of study drug infusion. Urine PK samples will be collected over the first 4 hours after start of infusion.

Approximately 4 weeks after the last eteplirsen infusion (regardless of the duration of the patient's participation in the study), patients will be required to return to the study site for safety evaluations. The total duration of patient participation, including Screening, Titration/Treatment, and Safety Follow-up periods is up to 101 weeks.

Refer to Section 10 for the detailed list of study assessments.

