8.4. Completion of a Patient's Participation in the Study

Patients are considered completers for the purpose of analysis once the Week 48 assessments have been completed. Patients may continue in the study up to and including 96 weeks based on the judgement of the Investigator (described further in Section 7.1); however, a Safety Follow-up visit will occur approximately 4 weeks after the last dose administered regardless of the patient's duration in the study. The length of a patient's participation will be from the time the informed consent form is signed until completion of the Safety Follow-up visit (approximately 4 weeks after the last dose is administered).

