## 4.5. Analysis Set

The Safety set includes all patients who are enrolled in Study 4658-102 and receive at least 1 dose of eteplirsen while in Study 4658-102. This analysis set will be used for analyses of all endpoints for the 4658-102 Final Analysis, unless stated otherwise.

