## 5. GENERAL STATISTICAL METHODS AND CONVENTIONS

## 5.1. General Methods

Summary statistics will be presented by cohort, unless stated otherwise.

For continuous variables, descriptive statistics will include the number of patients with data to be summarized (n), mean, standard deviation (SD), median, minimum, and maximum.

For categorical/qualitative variables, descriptive statistics will include frequency counts and percentages. The total number of patients in the cohort will be used as the denominator for percentage calculations, unless stated otherwise.

Summaries will be for the following cohorts:

- Cohort 1 (age 24 to 48 months)
- Cohort 2 (age 6 to <24 months)

safety s	et for the final analysis of 4658-1	102.	All analyses will be displayed on the
5.2.	Handling of Missing Data	a	
5.2.1			

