#### Treatment-emergent Adverse Event (TEAE)

An AE will be considered treatment-emergent if it starts in the time period starting with the initiation of the first dose of eteplirsen and ending 28 days after the last dose of eteplirsen.

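### The AE tables by year of treatment have no at-risk denominator, so Year 2 percentages are diluted if any child stops before about Week 50

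*SAP*

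**What the plan says.** SAP 6.8.1 adds to the standard AE output "summary tables of AEs by each one-year duration of eteplirsen", listed from the first year to the sixth. The same section says that AE tables, unless otherwise noted, give the number and "percentage of patients reporting AEs will be grouped using the MedDRA System Organ Class" and preferred term, overall and by age cohort.

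SAP 5.1 sets the denominator: "The total number of patients in the cohort will be used as the denominator for percentage calculations, unless stated otherwise". SAP 4.5 defines the Safety set as everyone enrolled with at least one dose and adds: "This analysis set will be used for analyses of all endpoints for the 4658-102 Final Analysis, unless stated otherwise". The visible text of 6.8.1 states no other denominator, at-risk count or exposure adjustment for the by-year tables.

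SAP 5.7 defines a treatment-emergent event as one that starts from the first dose, with the period "ending 28 days after the last dose of eteplirsen".

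Treatment length is not fixed. Protocol 8.4 says: "Patients are considered completers for the purpose of analysis once the Week 48 assessments have been completed". Protocol 7.1 allows treatment for "up to 96 weeks determined by the Investigator based on the absence of any safety signal and an indication of clinical benefit". The synopsis and 8.4 refer more generally to the Investigator's judgement. SAP 5.7 itself provides duration categories below 96 weeks.

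**The concern.** A by-year table invites the reader to compare Year 1 with Year 2. That comparison is fair only if each column counts children who could have had an event in that year. Under the stated default, a child who has left treatment and passed out of the treatment-emergent window is counted in Year 2 as a child without an event.

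Selection may act in the same direction. Under Protocol 7.1, continuation depends partly on the absence of a safety signal, so the children who leave may be those with the less favourable safety course. They would then appear as event-free in Year 2.

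Safety and tolerability is the primary objective and its analysis is descriptive, so these percentages are read directly, with no model behind them to correct the base. With about 6 children per cohort, each departure removes one sixth of those at risk.

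**Working it through.** The plan gives no Year 2 rate and no number continuing, so there is no stated figure to reproduce. Two direct calculations apply.

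**Inputs**
- One infusion every 7 days from Day 1, with a window of ±3 days (Protocol 9.2).
- Treatment-emergent period to 28 days after the last dose (SAP 5.7).
- About 6 children per cohort, about 12 overall (SAP 4.1).
- Assumption: Year 2 starts on Day 366. The SAP does not state the boundary.
- Assumption: k children reach Year 2. The documents give no number, so a range is shown.

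**1. Who can have a Year 2 event**

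The Week w dose falls on Day 1 + 7(w − 1), and the window closes 28 days later. The protocol's 101-week participation supports this convention: 2 + 95 + 4 = 101.

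| Last dose | Dose day | Window closes | Reaches Day 366? |
|---|---|---|---|
| Week 48 | 1 + 7×47 = 330 | 358 | No |
| Week 48, 3 days late | 333 | 361 | No |
| Week 49 | 1 + 7×48 = 337 | 365 | No |
| Week 50 | 1 + 7×49 = 344 | 372 | Yes, 7 days |
| Week 96 | 1 + 7×95 = 666 | 694 | Yes, 694 − 365 = 329 days |

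On the nominal schedule, a child whose last dose is on or before Day 337 cannot contribute a Year 2 treatment-emergent event. If a year is read as 52 weeks, Year 2 starts on Day 365 and a Week 48 stopper is still excluded.

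**2. Effect on the percentage**

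With x children having the event in Year 2, the default gives x/n and the at-risk percentage is x/k. The ratio is (x/n) / (x/k) = k/n.

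| n | k continuing | x | Default x/n | At risk x/k | Ratio k/n |
|---|---|---|---|---|---|
| 6 | 6 | 2 | 33.3% | 33.3% | 1.00 |
| 6 | 5 | 2 | 33.3% | 40.0% | 0.83 |
| 6 | 4 | 2 | 33.3% | 50.0% | 0.67 |
| 6 | 3 | 2 | 33.3% | 66.7% | 0.50 |
| 12 | 9 | 2 | 16.7% | 22.2% | 0.75 |
| 12 | 6 | 2 | 16.7% | 33.3% | 0.50 |
| 12 | 3 | 2 | 16.7% | 66.7% | 0.25 |

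**3. Length of Year 2**

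A full course gives 329 days of Year 2, or 329/365.25 = 0.90 patient-years. A Week 50 stopper gives 7/365.25 = 0.02. Both count as one child in x/k, so correcting the denominator alone does not make the years equal in length.

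**The case against.** **The dilution may never occur.** SAP 6.1 counts completion through Week 96 and treats earlier stopping as premature, so the final analysis is built around the full course. If every child continues, k = n and nothing is understated. This stands, and it makes the point conditional. It does not remove it: SAP 6.1 also plans to summarise those who stop early, and SAP 5.7 has duration categories for them.

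**The protocol may already override the default.** Protocol 13.1 bases AE percentages on values that are not missing, and SAP 7.1 reports no change from the protocol except removal of the interim analysis. But that rule defines no at-risk set by year, and a child off study with no AE record is not clearly a missing value. SAP 5.8 repeats the rule only for treatment-emergent abnormalities, a term that SAP 5.7 uses for laboratory, vital sign, ECG and ECHO findings. The whole-cohort denominator is therefore an inference from a general default, but it is the rule that the SAP states.

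**The year boundary is undefined.** This is true, and it should be fixed. If Year 2 began after 48 weeks, on Day 337, a Week 48 stopper would have some days in it (Days 337 to 358). That is not an ordinary reading of a one-year interval.

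**A rule may sit in removed text.** Tables to the sixth year cannot be filled from a 96-week study, and parts of the SAP are blacked out. This cannot be excluded. The point rests on the visible text and does not depend on Years 3 to 6.

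**The tables are minor.** They are supplementary and descriptive. Counts appear beside percentages, and disposition, exposure and listings let a careful reader recover much of the at-risk number. This limits the harm but does not make the printed percentage correct.

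**Conclusion.** The point holds in conditional form. Under the SAP as written, any child whose last dose falls before about Week 50 stays in a Year 2 denominator to which he cannot contribute, and each Year 2 percentage is then k/n of its at-risk value. With 3 of 6 continuing, that is a halving. The size rests on the assumed number continuing and on a boundary at Day 366.

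A reader might infer that the Year 2 percentages are certainly too low, or that the table must show improving tolerability regardless of the drug's effect. The documents support neither. There is no understatement if all continue, and a large enough rise still shows. For example, 1 of 6 in Year 1 followed by 3 of 4 continuing children in Year 2 prints 1/6 = 17% and then 3/6 = 50%. The comparison is biased towards apparent improvement, not bound to show it. The overall treatment-emergent AE tables and the Week 48 analysis are unaffected.

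This should be corrected before database lock, but it does not threaten the trial's main safety summary.

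**What to change.** In SAP 6.8.1, for the by-year tables:

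- State the year boundary, for example Days 1–365 and 366–730 from first dose.
- Use as denominator the patients whose treatment-emergent period reaches that year, and say that this replaces the default in 5.1.
- Print that N, the patient-years at risk and the events per patient-year in each column, by cohort and overall. Count patient-years at risk over the treatment-emergent period within the year. The exposure formula in SAP 5.7 adds 7 days after the last dose, not 28, so it does not give this figure. The rate is needed because a child with a few days in Year 2 otherwise counts the same as one with 329.
- Footnote that continuation past Week 48 was determined by the Investigator, based per Protocol 7.1 on absence of a safety signal and an indication of clinical benefit. The new denominator does not remove that selection.
- Optionally, add a Year 1 column restricted to children who reached Year 2.

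The cost is a paragraph of SAP text, one derived flag per year and a person-time calculation, all from dates already collected. Some Year 2 percentages may look less favourable. If every child continues, the percentages do not change.

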#### 6.8.2 Adverse Events of Special Interests

Summaries of TEAEs of special interest by SOC and PT will be summarized overall and by age cohort. All standard MedDRA queries (SMQs based on MedDRA version 17.1) listed below will include broad and narrow terms.

The AEs of special interest (AESI) are:

- Nephrotoxicity
  - $\circ$  Proteinuria > 500 mg/24 hr
  - $\circ$  eGFR <60 ml/min/1.73 m^2
- Hepatotoxicity
  - $\circ$  GGT or GLDH > 8 × ULN
  - GGT or GLDH >  $5 \times$  ULN for more than 2 weeks
  - $\circ$  GGT or GLDH > 3 × ULN and (total bilirubin >2 × ULN or international normalized ratio > 1.5)
  - GGT or GLDH > 3 × ULN with the appearance of the following signs or symptoms: fatigue, vomiting, right upper quadrant pain or tenderness, fever, rash, and/or eosinophilia (> 5%).
- Hypersensitivity
  - Anaphylaxis, anaphylactoid reaction, or angioedema
    - for Anaphylaxis use PT anaphylactic reaction, anaphylactic shock
    - for Anaphylactoid reaction use PT anaphylactoid reaction, anaphylactoid shock
    - for Angioedema use PTs angioedema, epiglottic oedema, laryngeal oedema, laryngotracheal oedema, lip oedema, swollen tongue, tongue oedema, tracheal oedema
  - Any severe allergic reaction (Hypersensitivity SMQ Broad & Narrow)
  - Any severe (Grade  $\geq$ 3) infusion related reactions (IRRs) that occurred within 24 hrs.

- Any severe complement mediated, inflammation event (eg, acute kidney injury, arteritis, myocarditis, pneumonitis)
- Thrombocytopenia
  - Platelet count  $< 75,000/\text{mm}^3$
- Infusion-related reactions
  - All adverse events with reported start time within 24 hours of the eteplirsen infusion if AE start clock time and infusion clock time is available OR occurred by the next calendar date if either AE start clock time or infusion clock time is not available.

An overall summary of adverse events of special interest include total number of events, number of SAEs, number of treatment-related events, number of unrelated events, number of mild events, number of moderate events, number of severe events, and number of events occurring on the same day as an infusion.

A corresponding listing will be generated for each table of AE of special interest. If applicable, a table corresponding to the adverse events of special interest that were related to study drug and/or moderate or severe will be produced.

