11.3.9. Adverse Events of Special Interest

Adverse events of special interest (AESIs) are AEs (serious or nonserious) that are of special scientific and/or medical interest, for which ongoing and rapid communication by the Investigator to the sponsor is appropriate.

AESIs for this study are listed below. All AESIs should be reported as AEs to the sponsor within 24 hours of awareness irrespective of adverse event seriousness. This includes the events below that are based on lab abnormalities, which should be translated to an appropriate adverse even t term at the time of reporting.

Nephrotoxicity

- Proteinuria > 500 mg/24 hr
- eGFR <60 ml/min/1.73 m²

Hepatotoxicity

- GGT or GLDH $> 8 \times ULN$
- GGT or GLDH > 5 \times ULN for more than 2 weeks
- GGT or GLDH > 3 \times ULN and (total bilirubin >2 \times ULN or international normalized ratio > 1.5)
- GGT or GLDH > 3 × ULN with the appearance of the following signs or symptoms: fatigue, vomiting, right upper quadrant pain or tenderness, fever, rash, and/or eosinophilia (> 5%)

Hypersensitivity

- Anaphylaxis, anaphylactoid reaction, or angioedema
- Any severe allergic reaction
- Any severe complement mediated, inflammation event (eg, acute kidney injury, arteritis, myocarditis, pneumonitis)

Thrombocytopenia

• Platelet count < 75,000/mm³

Infusion-related reactions

All infusion related reactions considered severe (see Section 11.3.4), occurring within 24
hours of the eteplirsen infusion, should be reported to the Sponsor within 24 hours of
awareness.

Infusion-related reactions may include headache, vomiting, diarrhoea, pyrexia, abdominal pain, upper, flushing and nausea. There may be pain at the site of the infusion as well as bruising surrounding the infusion site. Infections are also possible at the site of the infusion. All reactions grade 3 or higher, occurring within 24 hours of the eteplirsen infusion, should be reported to the Sponsor within 24 hours of awareness. Infusion-related reactions considered severe should be

reported to the Sponsor within 24 hours.

Rhabdomyolysis

Rhabdomyolysis adverse events of any severity.

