#### 6.8.3 Important Risks

Summarized overall and by age cohort. All standard MedDRA queries (SMQs based on MedDRA version 17.1) listed below will include broad and narrow terms unless noted.

- Nephrotoxicity:
  - o Acute renal failure SMQ
  - o HLT Glomerulonephritis and nephrotic syndrome
  - o HLT Nephritis NEC
  - o HLT Nephropathies and tubular disorder NEC
  - o PT Hematuria (10018867)
- Hypersensitivity
  - o Hypersensitivity SMQ
  - o HLT Immune response protein analyses NEC
- Infusion related reaction: events occurring within 24 hours of infusion or the next calendar day if the time (AE onset or start of infusion) is missing. Medical adjudication will be performed to determine whether the event is a possible infusion related reaction.
- Hypersensitivity excluding medically reviewed infusion related reaction: Hypersensitivity SMQ events minus events adjudicated as possible IRRs.

An overall summary of adverse events of important risks include total number of events, number of SAEs, number of treatment-related events, number of unrelated events, number of mild events, number of moderate events, number of severe events, and number of events occurring on the same day as an infusion.

A corresponding listing will be generated for each table of AE of important risks. If applicable, a table corresponding to the adverse events of important risks that were related to study drug and/or moderate or severe will be produced.

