## 7. CHANGES IN PLANNED ANALYSES

## 7.1. Changes from Clinical Protocol-Planned Analyses

Compared to the clinical protocol of 4658-102 (Version 4, dated 07 February 2020) the interim analysis 4658-102 is removed. There are no other changes in this SAP.

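### SAP 6.8.2 departs from the protocol's AESI set in two of six groups: its infusion-reaction category takes every AE within 24 hours of an infusion, and rhabdomyolysis is left out

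*SAP*

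**What the plan says.** Protocol 11.3.9 lists nephrotoxicity, hepatotoxicity, hypersensitivity, thrombocytopenia, infusion-related reactions and rhabdomyolysis. The infusion item is limited by severity: "All infusion related reactions considered severe (see Section 11.3.4"), within 24 hours of the infusion. The explanatory paragraph that follows puts the same limit as "grade 3 or higher, occurring within 24 hours of the eteplirsen infusion". The last item is "Rhabdomyolysis adverse events of any severity".

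SAP 6.8.2 has five groups. Its infusion-reaction group consists of "All adverse events with reported start time within 24 hours of the eteplirsen infusion" when both clock times are known, and otherwise of events that "occurred by the next calendar date if either AE start clock time or infusion clock time is not available". A separate line under Hypersensitivity takes severe (Grade 3 or higher) "infusion related reactions (IRRs) that occurred within 24 hrs". Rhabdomyolysis is not listed.

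Two other sections of the SAP touch the same events. Section 6.8.3 uses the same 24-hour window for an important risk called infusion related reaction, and adds: "Medical adjudication will be performed to determine whether the event is a possible infusion related reaction". Section 6.8.5 summarises rhabdomyolysis through the Rhabdomyolysis/myopathy SMQ, with broad and narrow terms.

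SAP 7.1 reports the removal of the interim analysis and then states: "There are no other changes in this SAP".

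**The concern.** The two documents use one label, AESI, for different sets of events. For infusion reactions the protocol asks for a clinical judgement (a reaction to the infusion) and a severity threshold. The SAP category asks only for timing. A cold or a fall that begins the evening after a weekly visit qualifies, and the overall AESI summary opens with the total number of events, so it enters that total.

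Safety is the primary endpoint, about 12 children are planned, and there is no control arm. No comparator rate is available to separate events that fall near an infusion by chance from reactions to it. An unfiltered category can suggest a reaction rate that is mostly calendar coincidence, and it can also bury a few real reactions among coincidental ones. Leaving out rhabdomyolysis errs the other way: a group that the protocol singles out is missing from the AESI total.

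A reader of the study report would also meet two infusion-reaction counts, one from 6.8.2 and one from 6.8.3. They agree only if adjudication accepts every event in the window.

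**Working it through.** The documents give no event rate or target figure on this point, so there is nothing to reproduce. The check is a comparison of the two lists, followed by an illustration of size.

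**Comparison of the AESI lists**

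| Group | Protocol 11.3.9 | SAP 6.8.2 |
|---|---|---|
| Nephrotoxicity | two laboratory criteria | same criteria |
| Hepatotoxicity | four laboratory criteria | same criteria |
| Thrombocytopenia | platelet threshold | same threshold |
| Hypersensitivity | three items | same three items, plus severe infusion reactions |
| Infusion-related reactions | severe reactions within 24 hours | any AE within 24 hours, or by the next date if a clock time is missing |
| Rhabdomyolysis | any severity | absent; in 6.8.5 by SMQ |

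The last two groups differ. The extra Hypersensitivity line is a by-product of the infusion-reaction difference: a severe infusion reaction qualifies under both SAP headings, whereas the protocol keeps the two groups apart.

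**Size of the timing effect**

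Inputs:
- One infusion every 7 days (Protocol 9.2).
- A 24-hour window (SAP 6.8.2).
- About 12 patients (Protocol 8.1).
- Assumed: background AE onsets are independent and spread evenly over the dosing week.
- Assumed: 10 background AEs per child, range 5 to 20. The documents give no figure.

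1. Share of the week in the window: 24 / (7 × 24) = 1/7 = 14.3%.
2. Chance that a child with k background AEs has at least one counted: 1 − (6/7)^k.
   - k = 5: 1 − 0.463 = 0.537
   - k = 10: 1 − 0.214 = 0.786
   - k = 20: 1 − 0.046 = 0.954
3. Expected number counted per child, k/7: 0.71, 1.43 and 2.86.
4. With k = 10 in each of 12 children: 12 × 0.786 = 9.4 children in the category, and 120/7 = about 17 events, with no true infusion reaction among them.
5. Upper bound, if a clock time were missing for every event: the infusion date plus the next date is 2/7 = 28.6% of the week, and at k = 10 the chance is 1 − (5/7)^10 = 0.965. Protocol 11.4 requires the time of onset to be recorded, so the rule should apply to some events at most.

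**The case against.** The strongest reply is that little is lost. Severe infusion reactions are on the SAP's AESI list, under Hypersensitivity. The overall AESI summary splits events by severity and by relationship to treatment, so background events judged unrelated would be shown as unrelated. The 6.8.2 window and the adjudicated 6.8.3 count can be read as a screen and its subset. Rhabdomyolysis has its own summary in 6.8.5, and all safety data are listed. The analyses are descriptive, and no test or stopping rule uses the AESI table.

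Most of this is correct, and it rules out three stronger readings that a reader might infer:

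- **That the SAP fails to report the protocol's severe infusion reactions.** It reports them under another heading.
- **That rhabdomyolysis is missing from the SAP.** It is missing only from the AESI section. The 6.8.5 query is wider than the protocol item, however, because it brings in myopathy terms in children who have a muscle disease.
- **That SAP 7.1 makes a false statement.** Protocol 11.3.9 defines AESIs for rapid reporting to the sponsor, and the AE tables planned in Protocol 13.8.2.1 include no AESI table. On that footing the SAP's AESI tables are additions, and no planned analysis was altered. What stands is that 7.1 is silent while 6.8.2 presents a set that differs from the protocol's under the same name.

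The reply does not remove the core. The severity and relationship splits are described for the AESI set as a whole, and they do not recreate the protocol's infusion-reaction group. The unfiltered events still enter the AESI total, and rhabdomyolysis still does not.

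**Conclusion.** The point holds for two of the six protocol AESI groups. Followed as written, SAP 6.8.2 labels every AE in the 24-hour window an infusion-related reaction of special interest, files the protocol's own infusion AESI under Hypersensitivity, and leaves rhabdomyolysis out of the AESI list. The other groups keep the protocol's criteria.

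Under even onset, 14% of background events enter the category by timing alone. The 79% chance per child (54% to 95%) also depends on the assumed 10 (5 to 20) background events. These figures describe the wide 6.8.2 category only. They say nothing about the severe-reaction line or the adjudicated count in 6.8.3. Onset may not be even: infusion-day vital signs and at least an hour of observation could draw recorded onsets towards infusion days, which would make 1/7 too low.

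A reader might take 2/7, or 2 × 120/7 = about 34 events, as the expected size. The documents do not support that, because it needs a missing clock time for every event.

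The correction should be made before the tables are produced, since these are safety results in a small uncontrolled study.

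**What to change.** In SAP 6.8.2:

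- Make severe infusion-related reactions within 24 hours, as in Protocol 11.3.9, their own AESI category. Move that line out of Hypersensitivity and link it to the adjudication in 6.8.3. State whether the 24 hours run from the start or the end of the infusion, since the protocol does not say.
- Keep all AEs within 24 hours of an infusion as a summary or listing that is labelled as timing only and does not count towards the AESI total. The next-date rule for missing clock times can stay there.
- Add rhabdomyolysis AEs of any severity to the AESI list, and keep the SMQ summary in 6.8.5 with a cross-reference.

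In SAP 7.1, record any difference from the protocol's AESI set that is intended.

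The cost is SAP wording and table labels. The adjudication is already planned and no new data are needed. The downside is a smaller infusion-reaction AESI count that depends partly on adjudication; the timing summary keeps the wider set of events visible.
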